- ^d V3 should be held after the patient has completed 12 days at minimum in the run-in period. Assessment of randomization criteria should be completed prior to taking blood samples or administering IMP to ensure that the patient qualifies to enter the treatment period. Daily lung function and diary compliance will be calculated electronically and should be assessed for compliance. At this visit the patient's diary data should be reviewed prior to formal lung function testing, laboratory testing and the various questionnaires to ensure compliance with diary entries and to determine if lung function, symptoms and rescue medication use meet the randomization criteria or if the patient should be considered to have failed randomization. Once all of the randomization criteria are met, the blood samples will be collected prior to randomization in the IRT system and IMP dosing.
- ^e V9 is the last visit during the double-blind treatment period. Patients who complete this visit should be advised regarding ongoing asthma maintenance treatment. Study provided rescue medication should be collected (albuterol/salbutamol). Patients who require a change in medication due to a CAE or to maintain asthma control (see alert criteria for worsening asthma) should complete V8 procedures prior to the change in medication whenever possible and these patients should continue participation for collection of lung function testing, questionnaires, blood samples and safety monitoring until the end of the study. If a change occurs after V8, the V9 procedures should be completed and the patient should enter the follow-up period.
- ^f Patients who withdraw consent or cannot participate in the remaining study assessments.
- ^g Results from the telephone follow-up calls should be recorded on the CRF and noted within the patients' source documents.
- ^h Informed consent should be obtained prior to any other study procedures.
- ⁱ Randomization via the IRT system should not be done until all lung function, questionnaires and clinical assessments have been completed to ensure that patients meet the study requirements and are appropriate for dosing.
- ^j The patient's history of asthma should be evaluated including duration, current medication, and history of exacerbations in the last year.

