9.5.4. Planned Method of Analysis

The mITT and PP analysis sets will be used for the efficacy analyses. The mITT analysis set will serve as the primary efficacy analysis population, while the PP analysis set will serve as the supportive population for the primary efficacy endpoint as well as the secondary efficacy endpoints.

Descriptive statistics (n, mean, standard deviation, standard error, median, minimum, and maximum for continuous variables, and patient counts and percentage for categorical variables) will be provided for each efficacy variable by visit or week, as appropriate. Summaries will be presented by treatment group.

All statistical tests will be conducted at the two-sided 0.05 significance level.

Unless otherwise specified, baseline value is defined as the last available value before the administration of IMP.

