The repeated measures logistic regression model with treatment group, corresponding baseline parameter value, prior therapy use, week, and week-by-treatment group interactions in the model and with an unstructured covariance matrix will be used. In the case of convergence issues with the unstructured covariance form, the exchangeable covariance matrix will be used. The weekly

probability estimates of achieving the improvement criterion in each treatment group, as well as the estimates of weekly odds ratios comparing each TEV-53275 treatment group versus placebo with corresponding 95% CI and p-values will be derived.

All repeated measures model will be run including measurements at all visits/weeks through week 16.

For changes from baseline in weekly average of rescue medication use over 12 weeks from week 1 through 12 and over 16 weeks from week 1 through 16, and changes from baseline in percentage of asthma control days (no symptoms and no rescue medication use) over 12 weeks from week 1 through 12 and over 16 weeks from week 1 through 16, Wilcoxon rank-sum test will be used stratified on randomization stratification factors.

The frequency of CAEs will be analyzed using a negative binomial regression method including randomization stratification factors and treatment group in the model and the logarithm of follow-up time as an offset variable. The ratio of CAE rate between the treatment groups and its 95% CI will be estimated from the negative binomial regression model. Treatment effects will be tested using the likelihood-based Chi-square test.

The Kaplan-Meier method will be used to estimate and compare the distributions of time to the first CAE between treatment groups. Distribution difference will be compared by a log rank test adjusting for the randomization stratification factors.

9.5.4.4. [REDACTED]

[REDACTED]

[REDACTED]

[REDACTED]

[REDACTED]

9.5.4.4.1. [REDACTED]

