5.3. Demographics and Baseline Characteristics

The demographic data will be collected at the screening visit after the patient signs the informed consent form. Patient demographic data including age, age group (<65 years vs \geq 65 years), gender, race, race group (white or other), ethnicity, baseline weight (kg), baseline height (cm), baseline body mass index (BMI; kg/m²), and baseline BMI group (<30 vs \geq 30), randomization stratification variables per IRT and per CRF: prior therapy (medium- and high-dose ICS alone and low-dose ICS/LABA vs. medium- and high-dose ICS/LABA), and absolute eosinophil count (300 to <400 cells/ μ L, or \geq 400 cells/ μ L) will be summarized using descriptive statistics for the ITT, safety, mITT, and PP analysis sets. In addition, baseline characteristics including asthma history and EGC findings at screening will be summarized for the ITT and safety analysis sets using descriptive statistics. No inferential analyses will be performed.

Asthma history includes

- Months since asthma diagnosis (derived)
- The duration of asthma
- The number of inpatient hospitalization due to asthma over the past 12 months
- Months since most recent inpatient event due to asthma (derived)
- The number of emergency department visit due to asthma over the past 12 months
- Months since most recent emergency department visit due to asthma (derived)
- the number of times oral or injectable corticosteroids were prescribed for asthma in the last 12 months
- Months since last prescription of oral corticosteroids for asthma (derived)

The month will be calculated as (date of informed consent - the date of the event + 1)/30.44. Rules for handling partial dates are in Section 4.3.

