6.3.8. Time to First Clinical Asthma Exacerbation (CAE) Throughout the Study

The time (days) to the first CAE is the interval from the randomization to the occurrence of the first CAE.

The observation for each patient is the interval from randomization to the occurrence of the first CAE, or censoring, whichever occurs earlier. It is derived as:

the date of censoring or the date CAE - the date of randomization + 1.

Patients who early terminated from the study without CAE due to lack of efficacy or an asthma-related AE will be also treated as experiencing CAE at the time of early withdraw visit.

Patients who complete the week 16 visit without CAE will be right-censored at the time of Week 16 visit. Patients without CAE and early withdrawn from the study before the week 16 with reasons other than lack of efficacy or asthma-related AEs will be right-censored at the time of early withdrawal visit.

The Kaplan-Meier (KM) method will be used to estimate and compare the distributions of time to the first CAE between treatment groups. Distribution difference will be compared by a log rank test adjusting for the randomization stratification factors.

[REDACTED]

6.3.9. Changes From Baseline in Asthma Control Questionnaire (ACQ-6) at Weeks 12 and 16

The ACQ-6 is a validated asthma assessment tool that has been widely used. The 6 questions are self-assessments (completed by the patient). Each item on the ACQ-6 has a possible score ranging from 0 to 6, and the total score is the mean of all responses. ACQ-6 will be administered at visit 2/run-in, visit 3/DoR, visit 5/week 2, visit 6/week 4, visit 7/week 8, visit 8/week 12, and visit 9/week 16 or early withdrawn visit.

The mean total score of the ACQ-6 is derived as the average of the individual item scores. For incomplete data, the following rules will apply:

1. Mean total score for a visit will not be calculated if Question 1 is left blank, irrespective of the completion of the remaining questions.
2. A missing score on post-baseline questionnaire for Questions 2-6 will be imputed based on the total scores from the previous visit, as long as at least 3 out of the 5 questions have responses for the current visit (ie, at least half of the remaining questions are answered).

The formula is: (total sum of non-missing scores for the current visit / total sum of scores for the previous visit for questions answered for the current visit) * (score for the missing question on the previous visit)

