7. MULTIPLE COMPARISONS AND MULTIPLICITY

No adjustments will be made for the preplanned multiple comparisons/endpoints.

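### Prior-year exacerbation history is collected but unused in the visible CAE analyses; prespecifying it as a covariate is a cheap, low-priority efficiency gain, not the correction of an error.

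*Protocol*

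**What the plan says.** **Collection.** Protocol 3.5, Table 2, footnote j says that at screening the patient's "history of asthma should be evaluated including duration, current medication, and history of exacerbations in the last year". Protocol Appendix B repeats this for Visit 1.

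**Use of the history.** SAP 5.3 lists 12-month counts of asthma hospitalisations and emergency visits, and "the number of times oral or injectable corticosteroids were prescribed for asthma in the last 12 months". They belong to the baseline table, for which "No inferential analyses will be performed".

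**Time to first CAE.** SAP 6.3.8 plans Kaplan-Meier curves, and "Distribution difference will be compared by a log rank test adjusting for the randomization stratification factors". On the window it says: "Patients who complete the week 16 visit without CAE will be right-censored at the time of Week 16 visit".

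**CAE frequency.** Protocol 9.5.4.3 plans a "negative binomial regression method including randomization stratification factors and treatment group in the model", with log follow-up time as offset.

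The two randomisation factors are maintenance therapy and screening eosinophil count (below 400 versus 400 cells/µL or more).

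**Error control.** Protocol 9.5.4: "All statistical tests will be conducted at the two-sided 0.05 significance level". SAP 7: "No adjustments will be made for the preplanned multiple comparisons/endpoints".

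**The concern.** A patient's recent exacerbations can be expected to predict the next one. The trial records them, then sets them aside when CAEs are compared. This departs from the plan's own pattern: of the 12 secondary efficacy endpoints, the other 11 use a baseline counterpart, either as a model term or through change from baseline.

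Eligibility does little to narrow the covariate. Inclusion criterion c asks only for 1 month without an exacerbation, so patients with none and with several in the past year can both enter.

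At stake is precision on an endpoint likely to have few events. When event rates vary between patients, a Cox or log-rank comparison that omits a measured part of that variation estimates a marginal effect that lies nearer the null than the within-patient effect, and has somewhat less power.

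**Working it through.** **1. The plan's own figure.** The only visible power figure whose inputs can be seen is for FEV₁ (SAP 2.4): 80.6% for an effect of 0.1 L, SD 0.35 L, one-sided alpha 15%. With 100 per arm less the 15% and 8% dropout in Protocol 9.1, 85 placebo and 92 active patients remain:

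- SE = 0.35 × √(1/85 + 1/92) = 0.0527
- power = Φ(0.1/0.0527 − 1.036) = Φ(0.863) = 80.6%

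It reproduces, but does not bear on CAEs. No CAE rate, hazard ratio or power is visible, so every CAE input below is an assumption.

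**2. How many events to expect.** For 100 versus 100 patients over 16 weeks (16/52 = 0.308 year), with constant rates and no dropout, expected first events = 100 × [1 − exp(−0.308r)] + 100 × [1 − exp(−0.308r × HR)]. Power is Φ(√(E/4) × |ln HR| − 1.96).

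| Placebo rate r per year | Events E, HR 0.5 | Power, HR 0.5 | Power, HR 0.7 |
|---|---|---|---|
| 0.2 | 9.0 | 18% | 8% |
| 0.5 | 21.7 | 36% | 14% |
| 1.0 | 40.7 | 60% | 23% |

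Events needed for 80% power = 4 × (1.96 + 0.842)² / (ln HR)², which is 66 at HR 0.5 and 247 at HR 0.7. The comparison is short of events with or without the covariate.

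**3. Gain from the covariate, moderate heterogeneity.** Assumptions: 92 per arm, patient rates gamma-distributed with shape 0.8, prior-year count Poisson at the patient's own rate, within-patient HR 0.5, censoring at week 16, two-sided 5%. Cox power without → with log(prior count + 1), over repeated runs:

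| Mean rate per year | Power without → with | Gain, points |
|---|---|---|
| 0.3 | 13.0 → 13.3; 13.5 → 12.6; 10.7 → 10.1 | +0.3, −0.9, −0.6 |
| 0.5 | 24.8 → 25.3; 23.8 → 25.2; 22.5 → 22.9 | +0.5, +1.4, +0.4 |
| 0.8 | 34.5 → 38.3; 34.0 → 37.6; 37.3 → 38.9; 35.1 → 37.8 | +3.8, +3.6, +1.6, +2.7 |
| 1.5 | 48.3 → 56.3; 48.0 → 55.6; 48.3 → 56.0 | +8.0, +7.6, +7.7 |

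With 1,500 trials, one power near 35% has standard error √(0.35 × 0.65/1500) = 1.2 points, so differences between runs are expected. At HR 0.7 the gain was −0.1 to +0.9 points. Type 1 error was 4% to 5% both ways (for example 4.9% without, 4.5% with).

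**4. Varying the heterogeneity.** 4,000 trials each, 100 per arm, 15%/8% dropout, likelihood-ratio tests, k = variance of the relative patient rate:

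| Rate per year | k | HR 0.5 | HR 0.7 |
|---|---|---|---|
| 0.2 | 1 | 18.2 → 17.7 | 9.3 → 9.2 |
| 0.5 | 0.5 | 30.9 → 31.4 | 13.1 → 13.5 |
| 0.5 | 1 | 29.4 → 30.1 | 12.4 → 13.1 |
| 0.5 | 2 | 26.0 → 28.4 | 10.9 → 11.7 |
| 1.0 | 0.5 | 50.3 → 51.6 | 19.1 → 19.2 |
| 1.0 | 1 | 45.4 → 48.4 | 17.2 → 18.5 |
| 1.0 | 2 | 36.5 → 44.2 | 13.4 → 17.5 |

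Twelve of these 14 comparisons lie between about −0.5 and +3 points. The two larger gains, about 4 and 8 points, are both at 1.0/year with k = 2.

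**5. Choice of test.** Likelihood-ratio and Wald tests are not interchangeable here. At 0.2/year, HR 0.5, k = 1, an adjusted Cox z-test reached 5.8% power against 15.0% for the plain log-rank. That loss comes from the Wald approximation with about 8 events, not from the covariate: an unadjusted Wald test falls in the same way.

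**6. Estimate.** At 1.5/year with a true within-patient HR of 0.50, the median Cox estimate was 0.55 without history and 0.52 with it. For the negative binomial rate ratio, a large-sample check with true ratio 0.5 gave 0.506 without and 0.502 with, so no material attenuation.

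**The case against.** The strongest reply is that nothing here is wrong: the analyses are valid and prespecified, and the gain may be nil. Most of this stands.

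- **Population.** Protocol 3.3 describes patients who do not meet severe-asthma criteria based on multiple exacerbations in the past 12 months. At shape 0.8, a rate of 1.5/year implies 35% of patients with two or more prior-year events, and 0.8/year implies 20%. No entry criterion enforces the description, but it points to the lower rates, where the gain is small.
- **Comparator.** The simulations leave the randomisation strata out of both analyses, although the protocol links eosinophils to exacerbation risk. They also assume a stable patient rate and error-free history. Both choices favour the covariate.
- **Longer follow-up.** A reader might cite larger gains over 30 weeks (for example 59.7% → 65.4% at 1.0/year, k = 1, HR 0.5). They do not apply: SAP 6.3.8 censors completers without a CAE at week 16.
- **Same events.** A reader might take the history items to be prior CAEs. They are related but not identical. Protocol 6.1.2 requires at least 3 days of systemic steroid, an emergency visit leading to systemic steroid, or hospitalisation. SAP 5.3 counts steroid prescriptions, emergency visits and hospitalisations separately, so one episode can appear three times.
- **Missing hazard ratio.** A reader might infer that none is planned. Text after the log-rank sentence and throughout SAP 6.4 is redacted, so this cannot be asserted.

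What the reply does not remove is that a plausible prognostic variable, already collected, has no visible role in the CAE comparisons, and prespecifying it needs no new data.

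**Conclusion.** The point holds as a modest efficiency suggestion. Under the planned week-16 censoring and HR 0.5, the change in Cox power is about 0 points at 0.5 events/year or fewer (about 2.5 at most in the scenarios run, with k = 2), 2 to 4 points at 0.8/year, and up to about 8 points at 1.5/year or with strong heterogeneity. At HR 0.7 it is mostly under 2 points. Rates, hazard ratios and heterogeneity are all assumed.

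Two stronger readings are not supported. The first is that the plan is biased, or leaves chance imbalance uncontrolled: the randomised tests already allow for chance imbalance, the Cox difference is between a conditional and a marginal hazard ratio, and the negative binomial ratio barely moves. The second is that material power is lost: the documents supply no rate from which to show it, and the endpoint stays underpowered either way. It is one of 12 secondary efficacy endpoints without multiplicity control, in a study whose success rule rests on FEV₁.

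Priority: low. Confidence: moderate.

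**What to change.** Before unblinding, amend the SAP to:

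1. Derive one prior-12-month exacerbation variable from the SAP 5.3 items, for example 0, 1, or 2 and more, with a rule against counting one episode under several items and a rule for missing history.
2. Add it as a covariate to the negative binomial model of Protocol 9.5.4.3, wherever the SAP specifies that model.
3. Add to SAP 6.3.8 a prespecified Cox model, stratified by the randomisation strata with the same covariate, reporting the hazard ratio and 95% CI. Prefer a likelihood-ratio test to a Wald test. Keep the Kaplan-Meier curves and the log-rank test as planned. Skip this step if redacted text already covers it.

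Putting the history into the log-rank as extra strata is less attractive, because strata become sparse with few events.

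**Cost.** No new data are needed, but the change is not free: it takes two derivation rules and some programming, the Cox hazard ratio becomes conditional on history, and the gain may be nil if events are few.

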4. SELECTION AND WITHDRAWAL OF PATIENTS

Prospective waivers (exceptions) from study inclusion and exclusion criteria to allow patients to be randomized/enrolled are not granted by Teva.

4.1. Patient Inclusion Criteria

Patients may be included in this study only if they meet all of the following criteria:

- a. The patient is capable of giving signed informed consent.
- b. The patient is an adult female or male ≥ 18 years of age. Note: Age requirements are as specified or allowed by local regulations.
- c. [Revision 1] The patient has a diagnosis of asthma for at least 6 months as defined by the National Institutes of Health (NIH) and has been stable without exacerbation or change in medications for at least 1 month.
- d. The patient has an absolute blood eosinophil count ≥ 300 cells/ μ L demonstrated during the screening period. Note: Rounding of the value (count) is not permitted.
- e. Severity of Disease: The patient has persistent asthma, with a trough FEV₁ $\geq 40\%$ and $\leq 85\%$ of the value predicted as per the National Health and Nutrition Examination Survey (Hankinson et al 1999, NHANES III 1998) and adjusted for ethnicity (Hankinson et al 2010). Note: Patients who do not qualify for the study due to failure to meet baseline spirometry or fail to achieve spirometry consistent with the American Thoracic Society (ATS)/European Respiratory Society (ERS) criteria (Miller et al 2005) will be permitted to perform repeat spirometry during the screening period on 1 occasion and if criteria are not met, will be considered to have failed screening.
- f. Reversibility of Disease: The patient has demonstrated reversibility of $\geq 12\%$ (increase) of FEV₁ and a minimum 200 mL increase from pre-albuterol/salbutamol FEV₁ approximately 30 minutes after 4 inhalations of albuterol/salbutamol hydrofluoroalkane (HFA) metered-dose inhaler (MDI) (90 μ g ex-actuator) or equivalent during the screening period.
- g. [Revision 1] Current Asthma Therapy: The patient has been maintained for at least 1 month on stable doses of:
 - medium or high dose ICS+another controller.
 - any fixed dose combination ICS (low, medium, or high) with LABA+another controller.
- h. Women of non-childbearing potential who are either surgically (documented hysterectomy, bilateral oophorectomy, or bilateral salpingectomy) or congenitally sterile as assessed by a physician, or 1-year postmenopausal (no menses for at least 12 months without an alternative medical cause plus an increased concentration of follicle stimulating hormone [FSH] of more than 35 U/L in women not using hormonal contraception or hormonal replacement therapy). Women of childbearing

potential must have a negative β -human chorionic gonadotropin (β -HCG) test result and practice a highly effective method of birth control (methods that can achieve a failure rate of less than 1% per year when used consistently and correctly) prior to IMP administration and 30 weeks after the dose of IMP. Highly effective contraception includes:

- combined estrogen and progestogen hormonal contraception (oral, intravaginal, transdermal) associated with inhibition of ovulation; these should be initiated at least 7 days before the first dose of IMP
- progestogen-only hormonal contraception (oral, injectable, implantable) associated with inhibition of ovulation; these should be initiated at least 14 days before the first dose of IMP
- intrauterine device (IUD) and intrauterine hormone-releasing system (IUS) need to be in place at least 2 months before screening
- bilateral tubal occlusion, except for hysteroscopic bi-tubal ligation for which a hysterosalpingogram (HSP) is required 3 months post procedure to assess surgical success
- vasectomized partner provided he is the sole sexual partner and has received medical assessment of the surgical success
- sexual abstinence is only considered a highly effective method if defined as refraining from heterosexual intercourse in the study period.

- i. The patient must be willing and able to comply with study restrictions and to remain at the investigational center for the required duration during the study period and the follow-up procedures and assessments as specified, and be willing to return to the investigational center for further visits, as applicable.
- j. The patient, as judged by the investigator, is able to continue their current asthma maintenance medications throughout the study.

4.2. Patient Exclusion Criteria

Patients will be excluded from participating in this study if they meet any of the following criteria:

- a. Life threatening asthma, defined as a history of asthma episode(s) requiring intubation and/or associated hypercapnea, respiratory arrest, hypoxic seizures, or asthma-related syncopal episode(s).
- b. The patient has a suspected bacterial or viral infection of the upper or lower respiratory tract, sinus, or middle ear that has not resolved at least 2 weeks before the screening period. Note: Patients who develop an upper respiratory infection/lower respiratory infection (URI/LRI) during the run-in period may rescreen 2 weeks after symptoms resolve and undergo coronavirus disease 2019 (COVID-19) testing as outlined in exclusion criteria “d”.

- c. Patients with a confirmed infection with COVID-19 within 3 months prior to the screening visit.
- d. Patients with clinical symptoms that may indicate COVID-19 infection, and/or patients who in the investigator's opinion were at high risk of exposure to COVID-19 within 4 weeks before screening or during screening/run-in, will be tested for active COVID-19 infection and will only be included if they test negative for COVID-19. For details of the management of study activities during COVID-19 outbreaks, see [Appendix N](#).
- e. The patient has an eosinophilic condition including hypereosinophilic syndrome, eosinophilic pneumonia, eosinophilic granulomatosis with polyangiitis (EGPA [Churg Strauss syndrome]), or allergic bronchopulmonary aspergillosis.
- f. The patient has an active helminthic or parasitic infection currently or within the last 6 months.
- g. The patient has a history of malignancy other than fully resected basal cell carcinoma of the skin.
- h. The patient has any clinically significant, uncontrolled medical or psychiatric condition (treated or untreated) that would interfere with the study schedule or procedures, interpretation of efficacy results, or compromise the patient's safety. (Note: chronic obstructive pulmonary disease [emphysema], bronchiectasis requiring treatment, cystic fibrosis, chronic bronchitis, and other diseases of the lung that may complicate interpretation of the study results are prohibited).
- i. The patient has known history of, or a positive test result for, hepatitis B surface antigen (HBsAg), hepatitis C virus (HCV) antibodies (Ab), or human immunodeficiency virus (HIV) Types 1 or 2 Ab (according to 4th generation serology testing).
- j. The patient is a pregnant or lactating woman, or plans to become pregnant during the study.
- k. The patient has taken prohibited prior medications within the washout period. Prohibited medications are listed in [Appendix G](#) with the appropriate washout periods.
- l. The patient has previously participated in a study with TEV-53275.
- m. The patient has participated in another study of an IMP (or a medical device) within the previous 30 days or 5 half-lives of the IMP (whichever is longer) or is currently participating in another study of an IMP (or a medical device).
- n. [Revision 1] The patient has been treated with a monoclonal antibody used to treat asthma or other inflammatory conditions within the washout period (5 half-lives), has demonstrated hypersensitivity or anaphylaxis to a monoclonal antibody ([Appendix G](#)), or is currently using or has used a systemic immunosuppressive medication within the last 6 months. NOTE: Prior depemokimab exposure is prohibited without exception.

- o. The patient has a known hypersensitivity to any components of the IMP stated or study supplied rescue medication.
- p. The patient has a history of chronic alcohol or drug abuse within the previous 2 years.
- q. [Revision 1] The patient currently smokes or has a smoking history of 10 pack years or more (a pack year is defined as smoking 1 pack of cigarettes [20 cigarettes]/day for 1 year), OR the patient used tobacco products within the past year (eg, cigarettes, cigars, chewing tobacco, or pipe tobacco), OR the patient has smoked marijuana within 1 month, OR the patient has a history of “vaping” tobacco, marijuana, or any other substance within 24 months.
- r. Vulnerable patients (eg, people kept in detention).

